- Patients will be given a functional test by a physical therapist preoperatively to get an initial starting point. The physical therapist will create a regimen for the patient to complete post operatively with an end point that is reachable based on the starting point. The length of time associated with reaching the end point will be captured.
- Patient employment will be documented. In addition a patient's leave from work will be recorded which may include things such as; short-term disability, vacation, or unpaid leave from work. The patient's salary will be requested and used to track the cost of missed time. If a patient elects not to disclose salary his or her zip code will be requested in order to find the median salary per that area. Worker's compensation claims may or may not factor into rehabilitation adherence and recovery time and will therefore be excluded from this study.
- A patient's return to work and function at work will be logged. The information will be compared based on procedure type.
- The time it takes a patient to return to driving will be tracked. In addition if the knee replacement procedure was performed on the left leg or right leg will be documented because this could factor into time it takes to return to driving. The length of time to return to driving will be reported by procedure type.
- The procedural costs of the different type of knee replacement allocated into different cost centers. The charges, costs, and reimbursements will also be examined and the data be gathered from the hospital accounting software.

Inclusion Criteria:

Study Design Patients will be recruited into the study under the direction of one of the principal investigators or qualified team members during regularly scheduled clinic visits. All patients over 21 years of age who require knee replacement surgery will be asked to participate in the study. These patients will have failed non-operative management of their joint disease and are candidates for partial joint replacement because of pain and joint stiffness that interferes with their performance of normal daily activities.

- Age, 21-80 years
- Sex, males and females will be included
- BMI less than or equal to 39
- Stable health, the patient would be able to undergo surgery and participate in the follow-up program based on physical examination and medical history
- Patient is willing and able to cooperate in follow-up therapy at Rebound facilities

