The study investigator will evaluate the patients for study inclusion/exclusion at their perioperative consultation visit. The surgeon will describe the various surgical options that he believes to be appropriate for each individual patient. The patient and surgeon then will determine which prosthesis is most appropriate for their surgical procedure. Then the surgeon or his assistant will explain the study to the prospective participant. Prospective participants will be encouraged to ask questions regarding study participation. Once they are fully informed about the study, the interested patients will be asked to sign a consent form.

Evaluation to be used for Knee Replacement Patients:

At each clinic visit which coincides with a study interval (preoperative, 2 weeks postoperative, 6 weeks, 3 months, 6 months and 1 Year) the surgeon or qualified member of the study will

- Assess the function and range of motion of the knee joint
- Document any complications that may have occurred after surgery
- Complete a radiographic assessment of the operated knee post-operatively per surgeon standard of care.
- Complete the Knee Society Score in order to provide a rating of the pain, function, range of motion, and knee joint stability for each patient
- Study participants will be asked to complete standardized health-related quality of life instruments to document their perception of their pain and function. Study participants will complete the following outcome instruments. These instruments can be completed via phone, mail, website, or email if a clinic visit is not required at the study interval per surgeon standard of care.
 - a) The American Knee Society Score is subdivided into a knee score that rates only the knee joint itself and a functional score that rates the patient's ability to walk and climb stairs[2].
 - b) The EQ-5D is a standardized instrument for use as a measure of health outcome. Patients will be also given a questionnaire with questions pertaining to employment, loss of wages, driving, etc.
 - c) The Reduced WOMAC is a truncated version of the Western Ontario and McMasters University Osteoarthritis Index. The questionnaire is patient administered and designed to assess pain, disability and joint stiffness in the OA patient[3].

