 - d) The KOOS or Knee injury and Osteoarthritis Outcome Score is a patient completed questionnaire to assess the patient's opinion regarding their knee and its associated OA. Poor outcomes are reported with a lower score and good outcomes with a higher score [4-7].
 - e) Post-op, the Forgotten Joint Score is a 12-item questionnaire completed by the patient to determine how aware they are of their joint in their everyday life[8].
- Post-op patients will complete a “progress report” regarding their satisfaction and rehabilitation.
- At 6 weeks post-op, patients will also be asked to complete a “return to function” questionnaire regarding their rehabilitation including their return to work and driving and physical therapy regimen. This questionnaire can be completed via phone, mail, website or email if a clinic visit is not required per surgeon standard of care.

In addition to regularly prescribed physical therapy, patients will meet with a physical therapist or qualified member of the study preoperatively for testing to create a starting point. They will also undergo multiple tests/ measurements at 6 weeks and 3-months postoperatively. The physical therapist will create a physical therapy regimen and create an endpoint for the patient. The endpoint will be goals within reach for each patient to complete before the patient can discontinue physical therapy.

- The patient will undergo a series of tests to create an initial starting point preoperatively and post operatively at 6 weeks and 3 months. The tests will be the following:
 - Timed up and Go (TUG) Test: Participants are instructed to stand up from a seated position from a standard chair, walk 3m around a cone and then return to the chair and resume a seated position. Pace is self-selected. The time to complete the test is recorded.

- 6 Minute Walk Test (6MWT) : Participants are instructed to cover as much distance walking in 6 minutes and can stop and rest if necessary. The course is 30 meters in length, marked at 1 meter intervals with cones marking the turnaround point. Distance measured is rounded up to the nearest meter and recorded.
 - Stair Ascend/Descend Test: Participants are asked to ascend and descend 11 steps using a hand rail if necessary. Stair height is 17.8 cm (7"). Pace is self-selected. The time to ascend/ descend 1 flight of stairs is recorded.

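### Return to work and driving: the only named form is charted once, at 6 weeks; later capture is plausible but unassigned, and no rule covers patients not yet returned

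*Combined protocol and SAP*

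**What the plan says.** The Objectives list two comparisons: time to return to work and time to return to driving. Recovery time is also in the Specific Aim.

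The Endpoints section gives no form and no end date for either. It says that a patient's "return to work and function at work will be logged" and, for driving, "The time it takes a patient to return to driving will be tracked". A patient's "leave from work will be recorded which may include things such as; short-term disability, vacation, or unpaid leave from work" is also to be recorded, with salary used to cost the missed time.

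The section on evaluation of knee replacement patients describes three possible sources:

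- **Return to function questionnaire.** Given at 6 weeks, a "questionnaire regarding their rehabilitation including their return to work and driving and physical therapy regimen". Its row in the Time and Events Chart has a single mark, under 6 weeks.
- **Unnamed questionnaire, item b (the EQ-5D item).** "Patients will be also given a questionnaire with questions pertaining to employment, loss of wages, driving, etc". The list it belongs to applies to each "study interval (preoperative, 2 weeks postoperative, 6 weeks, 3 months, 6 months and 1 Year"). It has no chart row of its own.
- **Progress Report.** A form "regarding their satisfaction and rehabilitation", charted at 6 weeks, 3 months, 6 months and 1 year.

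Data Analysis names means, standard deviations and ranges for continuous variables. General Statistical Considerations adds two-sided testing at 0.05. Neither says how a patient who has not yet returned is to be handled.

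**The concern.** A return time is known only once the patient has returned. If the one charted Return to function visit is the only time it is asked, a patient still off work or not driving at 6 weeks contributes a right-censored time. A plain mean and SD cannot use such a time. The analyst must drop the patient or enter 6 weeks, and the plan does not say which. Both choices shorten the apparent time, usually by more in the slower group, so the comparison between procedures is distorted.

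The plan itself allows for recovery beyond 6 weeks. Functional tests are repeated at 3 months, and there is an 8-week rule for patients who have not met the physical therapy discharge criteria. Nothing similar is written for work or driving. Missed work time also feeds a cost result, so truncated leave data would carry over to that.

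**Working it through.** **Which form holds the dates**

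| Source | Said to cover work and driving? | Charted after 6 weeks? |
|---|---|---|
| Return to function | Yes, by name | No |
| Item b questionnaire | Employment, wages and driving; return dates not mentioned | No row; may travel with the EQ-5D, charted to 1 year |
| Progress Report | Not by name; covers rehabilitation | Yes, to 1 year |

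The description of the Return to function form treats return to work and driving as part of rehabilitation. A Progress Report on rehabilitation could therefore include them. The form contents are not in the documents, so this cannot be settled from the text.

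**What a 6-week cutoff would do**

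The documents give no return times, so there is no plan figure to reproduce and every input below is assumed except the cutoff c = 6 weeks. Return time is taken as lognormal with median m and log-SD s. Write z = (ln c − ln m)/s.

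- True mean: M = m·exp(s²/2)
- Mean among those returned by c: M·Φ(z − s)/Φ(z)
- Mean with the rest set to c: M·Φ(z − s) + c·(1 − Φ(z))

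Worked case: 20% of the slower group not back at 6 weeks, s = 0.5 in both groups, ratio of medians 1.5.

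- Slower median: exp(ln 6 − 0.5 × 0.842) = 3.94. Faster median: 3.94/1.5 = 2.63.
- True means: 4.46 and 2.98, difference 1.49 weeks.
- Returners only: 4.464 × 0.634/0.800 = 3.54 and 2.976 × 0.875/0.951 = 2.74, difference 0.80 weeks (53% kept).
- Rest set to 6 weeks: 4.03 and 2.90, difference 1.13 weeks (76% kept).

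Repeating this for s = 0.3, 0.4, 0.5 and 0.6:

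| Slower group not back at 6 weeks | Kept among returners | Kept if rest set to 6 weeks |
|---|---|---|
| 5% | 76-88% | 91-97% |
| 20% | 48-68% | 71-86% |
| 50% | 23-42% | 39-62% |

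**Unequal spread** (second group minus first, in weeks)

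| Medians | Log-SDs | True | Returners | Rest set to 6 |
|---|---|---|---|---|
| 6 / 7 | 0.4 / 0.5 | +1.43 | −0.09 | +0.15 |
| 5 / 6 | 0.6 / 0.4 | +0.51 | +0.77 | +0.66 |
| 5 / 8 | 0.4 / 0.7 | +4.80 | −0.19 | +0.54 |
| 5 / 6 | 0.8 / 0.4 | −0.39 | +1.17 | +0.83 |

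The first row shows that a modest inequality is enough to reverse the sign among returners. The second shows an overstatement. In the first and third rows the sign reverses among returners only; setting the rest to 6 weeks keeps it right. In the fourth it reverses under both.

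**With dates to 52 weeks**

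Seven equal-spread cases were examined (medians from 2/3 to 6/9 weeks, log-SD 0.3 to 0.5). All keep at least 99.7% of the true difference, even among returners. The 5/6 case with log-SD 0.8/0.4 keeps 73% among returners and 93% as a restricted mean. Collecting the dates removes most of the problem, and the choice of summary deals with much of the rest.

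**The case against.** The strongest reply is that a 6-week cutoff is only one reading, and perhaps not the most natural. Item b places employment and driving questions among instruments given up to 1 year. The Progress Report covers rehabilitation to 1 year, and the protocol uses that word to include return to work and driving. The Timeline continues data collection until 1-year data are in for all participants. Costing missed work would be hard if recording stopped at 6 weeks. All of this stands. A reader might infer from the chart that nothing about return is collected after 6 weeks; the documents do not support that.

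A reader might also infer that the bias always shrinks the difference, or that a sign reversal needs very unequal spread. The unequal-spread cases above show that neither holds.

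It is also fair that the scenario figures rest wholly on assumptions, and that these are two among many unranked objectives in a minimal-risk, mainly descriptive study. That limits the severity. It does not answer the remaining gap: no text assigns the return dates to a form and visit after 6 weeks, and no rule covers patients who have not returned by their last contact.

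**Conclusion.** The point holds as a gap in schedule and analysis, of minor to moderate severity. It is certain that the only named form for these endpoints is charted once and that no rule exists for patients not yet returned. It is not certain that capture stops at 6 weeks.

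If it does stop there, the planned summaries are biased by an amount the documents do not allow anyone to state. The 48-68% and 71-86% figures assume lognormal times, equal log-SD of 0.3 to 0.6, a median ratio of 1.5 and 20% of the slower group not back. With unequal spread the direction is not predictable either. Work and driving may behave differently.

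If later capture already exists, the schedule causes no bias. What remains is to show it in the chart and to choose a summary that handles patients not returned by 1 year or lost to follow-up.

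None of this addresses confounding: "The patient and surgeon then will determine which prosthesis is most appropriate for their surgical procedure", so a difference between procedures would still need cautious reading.

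**What to change.** 1. State which form records the two return dates, and which form and visits carry the item b questions.
2. Unless already there, add the date returned to work and the date returned to driving to the Progress Report at 6 weeks, 3 months, 6 months and 1 year, asked until the event occurs. Show this in the Time and Events Chart.
3. Replace the mean and SD for these two endpoints with text such as:

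> Among patients who worked (or drove) before surgery, time from surgery to return, censored at last contact with known status, will be summarised by restricted mean time not yet returned to 52 weeks. The difference between procedure types will be given with a 95% CI. For work, retirement before return will be treated as a competing event from the outset: cumulative incidence of return will be shown by procedure type, and the restricted mean will be computed from that curve, so patients who retire count as not returned to 52 weeks.

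This fixes one method in advance, gives a between-group contrast, and does not switch method according to the data.

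The cost is at most two extra questions per visit on a form already charted to 1 year, one chart entry, and slightly more analysis work.

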- Patient has stable and functional collateral ligaments
- Patient or patient's legal representative has signed the Informed Consent form
- Failed non-operative management of their joint disease
- Need to obtain pain relief and improved function
- Moderate or severe pain with either walking or at rest
- Diagnosed with osteoarthritis in one or more compartments of the knee and non-surgical treatment options have failed to provide relief for symptoms

- Patient exhibits preoperative radiographic evidence of joint degeneration that cannot be treated in non-operative fashion

Exclusion Criteria:

Patients will be excluded from study participation if they are cognitively unable to complete study health-related quality of life forms and pregnant women are also excluded from participation in this study.

- Patients who, in the opinion of the Investigator, have an existing condition that would compromise their participation and follow-up in the study
- Patients with pre-op flexion contracture greater than 10 degrees, overall flexion less than 115 degrees, and varus/valgus greater than 10 degrees
- Patient who is on workmen's compensation
- Patients who are on chronic long acting preoperative narcotic pain medication
- Patients with inflammatory polyarthritis
- Women who are pregnant
- Subjects who are known drug or alcohol abusers or with psychological disorders that could affect follow-up care or treatment outcomes
- Subjects who are currently involved in another clinical study with the exception to an outcomes study
- Patients with a pathology which, in the opinion of the Principal Investigator, will adversely affect healing
- A diagnosed systemic disease that would affect their welfare or the overall outcome of study (i.e. Paget's disease, renal osteodystrophy)
- Patients receiving an isolated patellofemoral UKA, lateral UKA, or bi-compartmental arthroplasty
- Patients with significant medical condition preventing a well-functioning contralateral knee

Risk/Benefits:

This is a minimal risk study which involves collection of data. The purpose of this study is for research purposes only. There is no direct benefit to the patient to participate in this study. The results of this research study may contribute to clinical research overall and may be published.

Study Enrollment Procedure:

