Financial data will be obtained from each facilities cost accounting system. If data cannot be attained using this method, CPT codes will be recorded and cross-referenced with the 2010 Medicare Fee Schedule. The financial data will be estimated using this method. The use of Medicare reimbursement rate is reasonable given that more than 60% of arthroplasty cases are reimbursed by this agency. A patient's analgesic use will be recorded by the surgeon and the Average Wholesale Price will be assigned to each script. Discharge data collected in this study will be compared to 2006 National Hospital Discharge Survey (NHDS).

Data Management:

All data will be collected using data collection forms or questionnaires in clinic or via phone, mail, website or email. The data dependent upon the questionnaire or form will be recorded by the patient, investigator, or qualified team member. Information will then be entered into a secure online data entry system by a qualified team member and the data will be stored in a secure database. Numerous business rules ensure that only properly formatted data is submitted. The information undergoes further verification by a human operator, who checks the integrity of each record prior to submitting it to the database. All access to the information- including reports, queries and data tools- is password protected and restricted to users that have the proper credentials. Information pertaining to cost data will be uploaded separately into the database.

Data Analysis:

Descriptive statistics consisting of frequency tables and percent for categorical variables and means, standard deviations, and ranges for continuous variables will be tabulated at the conclusion of the study.

General Statistical Considerations:

Tabulation of summary statistics, graphical presentations, and statistical analyses will be performed using SAS® software. The primary presentations and analyses will be based on data pooled across study centers. Relevant summaries for individual centers, or combinations of centers, may be presented for primary data. All patient data will be presented in separate data listings. All patients who are enrolled in this study and receive any of the treatments as part of this study will be included in the safety analysis. All testing and confidence intervals will use a 0.05 significance level. All testing is two sided unless otherwise noted.

Patient Characteristics:

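### The TUG and stair tests record only a completion time, so patients physically unable to finish leave the summary by default; record inability and keep those patients in any comparison (minor)

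*Combined protocol and SAP*

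**What the plan says.** The section Evaluation to be used for Knee Replacement Patients lists three functional tests and gives their timing: "The patient will undergo a series of tests to create an initial starting point preoperatively and post operatively at 6 weeks and 3 months".

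- **TUG:** "The time to complete the test is recorded".
- **Stairs:** "Participants are asked to ascend and descend 11 steps using a hand rail if necessary", and then "The time to ascend/ descend 1 flight of stairs is recorded".
- **Six-minute walk:** "Participants are instructed to cover as much distance walking in 6 minutes and can stop and rest if necessary". The outcome is a distance, so a patient who stops early still has a value.

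The Data Analysis section plans "means, standard deviations, and ranges for continuous variables will be tabulated at the conclusion of the study". Neither section gives a maximum time, a rank, an inability code or a reason field for the two timed tests, and the document has no missing-data rule.

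**The concern.** A mean of times cannot include a patient who has no time. In the two timed tests, a patient who tries and cannot finish is among the worst results at that visit, and that patient is the one who disappears. The six-minute walk in the same list does not have this gap.

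Some inability is foreseeable. The Inclusion Criteria require "Moderate or severe pain with either walking or at rest", and the first postoperative test is at 6 weeks. A patient unable before surgery but able afterwards has no change score, so some large gains would be lost too.

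The Specific Aim is to compare recovery and outcomes between two procedures, and under Study Enrollment Procedure the patient and surgeon choose the prosthesis. The share unable could therefore differ between groups, before as well as after surgery. If it does, the groups are compared on different selections of patients. If the reason for a missing time is not written down at the visit, it may not be recoverable later.

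**Working it through.** The documents state no sample size, effect size, SD or completion rate, so there is no figure of the plan's own to reproduce. Everything below illustrates size under assumptions and is not an estimate for this trial.

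**Stair test, log-normal times.** Suppose each patient has a latent time T with median m and log SD s, and cannot finish if T exceeds a limit c. With k = (ln c − ln m)/s:

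- share unable = 1 − Φ(k)
- mean over all patients = m·exp(s²/2)
- mean over finishers = m·exp(s²/2)·Φ(k − s)/Φ(k)
- second moment over finishers = m²·exp(2s²)·Φ(k − 2s)/Φ(k), which gives the finishers' SD

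Worked case: s = 0.5, c = 60 s, medians 20 s and 25 s.

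- Faster group: k = ln(3)/0.5 = 2.197, so 1.4% are unable. The full mean is 22.66 s and the finishers' mean is 21.95 s.
- Slower group: k = ln(2.4)/0.5 = 1.751, so 4.0% are unable. The full mean is 28.33 s and the finishers' mean is 26.40 s.
- The difference falls from 5.67 s to 4.44 s (rounded from unrounded means), a loss of 22%.
- The pooled SD (root of the average variance) falls from 13.67 s to 11.03 s. The standardised difference therefore goes from 0.414 to 0.403, a loss of 3%.

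| s | Medians (s) | Limit (s) | Unable | Difference, all → finishers (s) | Raw loss | Standardised, all → finishers | Loss |
|---|---|---|---|---|---|---|---|
| 0.4 | 20 / 25 | 60 | 0.3% / 1.4% | 5.42 → 4.94 | 9% | 0.530 → 0.527 | 1% |
| 0.5 | 20 / 25 | 60 | 1.4% / 4.0% | 5.67 → 4.44 | 22% | 0.414 → 0.403 | 3% |
| 0.5 | 20 / 30 | 60 | 1.4% / 8.3% | 11.33 → 8.15 | 28% | 0.736 → 0.721 | 2% |
| 0.5 | 20 / 25 | 45 | 5.2% / 12.0% | 5.67 → 3.37 | 41% | 0.414 → 0.374 | 10% |
| 0.5 | 20 / 30 | 45 | 5.2% / 20.9% | 11.33 → 5.94 | 48% | 0.736 → 0.662 | 10% |

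The raw loss is large because the long right tail carries much of the mean. The standardised loss is small because cutting the tail also shrinks the SD.

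**Cross-check, normal times.** Take a true difference of 0.5 SD and a common limit, with z the limit in SD units for each group and λ = φ(z)/Φ(z). The observed difference is 0.5 − λ(slower) + λ(faster).

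- With 5% against 12.6% unable: 0.5 − 0.237 + 0.109 = 0.372, a loss of 26%.
- From 1% against 3.4% up to 10% against 21.7%, the observed difference runs from 0.449 to 0.319, a loss of 10% to 36% in units of the full SD.
- Dividing by the finishers' own SD (variance 1 − zλ − λ², averaged over groups) gives 0.475 down to 0.400, a loss of 5% to 20%.

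The direction agrees with the first model, and the standardised size depends on the shape assumed. In neither model does the gap reverse.

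**Speed with unable = 0.** Take speed as 22 steps (11 up, 11 down) divided by time. The finishers' mean speed is (22/m)·exp(s²/2)·Φ(k + s)/Φ(k); multiplying by Φ(k) counts the unable as zero. In the last row of the table the group difference is 0.415 steps/s on full latent speed, 0.343 among finishers and 0.473 with zeros. Over the five rows, the zero-imputed difference is 4% to 38% above the finishers-only one. Against the full latent difference, it overshoots by 1.5% to 13.9%, while the finishers-only one falls short by 2.8% to 17.5%.

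No such calculation was made for the TUG.

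**The case against.** The documents do not say that non-finishers are excluded. They are silent, and the test form is not among them, so it may already have an inability field. A reader might infer a written finishers-only rule; none exists. Exclusion is only what follows if the text is applied as it stands.

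The tests' role is also limited. The Endpoints section uses the preoperative functional test as a starting point and captures the time taken to reach the therapy goals. It does not name TUG or stair time as a comparison by procedure type. The objective on functional scores may refer to the Knee Society function score.

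Inability is partly seen elsewhere. The Knee Society function score covers walking and stairs at every interval. Stairs and gait are checked at each therapy visit until discharge. Function is also noted for patients who stop therapy at 8 weeks without meeting the goals.

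Non-completion may be rare. Pace is self-selected with no stated time limit, and a handrail is allowed on the stairs. Eligibility requires stable health, limits BMI, and excludes marked contracture, poor flexion and conditions that compromise the other knee. The 45 s and 60 s limits are assumptions, and 21% unable is an extreme case.

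All of this stands and lowers the priority. It does not close the gap, because none of the other measures enters the TUG or stair summaries and no rule links them.

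**Conclusion.** The concern holds in a limited form. As written, a patient physically unable to finish the TUG or stair test has no value and by default leaves the mean, SD, range and any change score. If inability differs between UKA and TKA, the finishers-only difference is biased, usually toward a smaller gap.

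The size rests wholly on assumed inability rates. With 0.3-5% against 1-21% unable and log-normal stair times, the loss is about 9-48% in raw seconds but about 1-10% in standardised units. It is negligible if nearly everyone finishes.

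A reader might infer that the slower-recovering group would come out ahead, or that the study's main comparison rests on these tests. The documents support neither: the gap shrinks without reversing in these models, and TUG and stair time are not named as comparisons by procedure. Minor priority.

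**What to change.** 1. At each TUG and stair test, record one of three states: completed, physically unable, or not done for another reason.
2. Report the percentage physically unable by procedure type preoperatively, at 6 weeks and at 3 months.
3. Where these tests are compared by procedure, prespecify an analysis that keeps the physically unable as the worst outcome. A rank-based comparison, or a median with the unable ranked slowest, would serve. So would speed with unable = 0, which also gives a change score to a patient unable at one visit.
4. Treat tests not done for other reasons as missing, and show mean time among finishers as a descriptive line.

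The cost is one form field and a short addition to the analysis text. A rank or speed result is less familiar than seconds, and speed with zeros may slightly overstate the latent difference, as shown above. No treatment or clinical rule changes.
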